9.4.2. The Optum Dynamic Assessment of Pregnancies and Infants

The cohorts for this study will employ DAPI, a proprietary process that includes a set of capabilities and established algorithms that is applied to claims data to identify pregnancies, trimesters, and pregnancy outcomes, and to link mothers' and infants' data in an ongoing manner, within the ORD (Bertoia et al. 2022). The algorithms are based on a combination of validated algorithms as reported in the literature and clinical input. Mother and infant records will be linked through the presence of a common unique family insurance ID. This number is used by health plans to identify all members of a family who are covered by the same insurance plan for the purposes of defining coverage, payment, and reimbursement, providing assurance that mother-infant pairs identified in this manner are accurate. In addition, claim(s) relating to the delivery must be within 7 days of the infant's birthdate (or 32 days for multiples).

In comparison with the broader US population, the women of child-bearing age who are included in the ORD (and DAPI) tend to be healthier, reflecting the underlying population of the commercial insurance enrollees, and likely have an age distribution more skewed toward older age, reflecting the age distribution of women within the work force.

Historically, there are approximately 200,000 pregnancies identified each year within the database, of which 80% (with observed outcomes) result in livebirths, 85% of which can be linked to an infant within the database. These linkages enable proactive monitoring of pregnancy outcomes to ascertain a range of outcome-specific risks associated with drug exposure during pregnancy. This linkage has been used to address regulatory questions by pharmaceutical companies about the effects of drugs on pregnancy (Cole & Modell et al. 2007, Cole & Ephross et al. 2007, Carman et al. 2017, Wyszynski et al. 2016).

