9.5. Study size

The planned sample size incorporates several assumptions derived from published literature, including the following approximate prevalence of pregnancy outcomes:

- Under 1% of pregnancies result in stillbirth (FDA 2002)
- 14% of pregnancies result in SA or miscarriage (FDA 2002)
- 18% of pregnancies have historically been expected to end in induced termination (Jones et al. 2017)
- 3% of live born infants have a major birth defect in the US each year (March of Dimes 2015)
- 10% of live born infants are born preterm or SGA (CDC 2008, Ferré et al. 2016)

Based on these reference percentages, the following assumptions were made for sample size calculation:

- $\alpha = 0.05$
- Power=0.8
- 1:2 matching
- Outcome prevalence as cited above

Table 1 and Table 2 show the minimum required number of PAXLOVID-exposed pregnancies required to proceed to the secondary objective of comparative analyses. Comparative analyses will be conducted if the sample size to detect a RR > 2.0 is achieved for each outcome; target sample size may be achieved for some outcomes but not others.

To detect a RR > 2.0 at 80% power a minimum of 127 PAXLOVID-exposed pregnancies are required for SA, 251 for SGA and preterm birth, and 2,212 for stillbirth, the rarest of the outcomes (Table 1). A minimum of 938 PAXLOVID-exposed pregnancies during the first trimester are required for the primary outcome of MCM (Table 2).

Fewer PAXLOVID-exposed pregnancies are required to detect an RR of > 2.5 at 80% power: 63 for SA, 127 for SGA and preterm birth, and 1,142 for stillbirth. For MCM, the minimum number of pregnancies with PAXLOVID exposure during the first trimester is 482. These estimates are based on 1:2 matching; however, the analyses for this study will utilize IPTW for confounding adjustment. Sample size calculations are based on 1:2 matching as a conservative estimate due to the retention of all eligible pregnancies in IPTW. Power for the analysis of induced termination will be similar to that for SA. The majority of pregnancies end in livebirth; therefore, power is expected to be adequate for this outcome.

Table 1. Sample Size Required for 80% Power to Detect Relative Risks (As or More Extreme) for Pregnancy Outcomes, with 1:2 Matching

Outcome	Prevalence of Outcome	RR	PAXLOVID-Exposed Pregnancies with Observed Outcomes Needed*	PAXLOVID-Exposed Pregnancies Needed**
SA	14%	2	101	127
		2.5	50	63
Stillbirth	1%	2	1,769	2,212
		2.5	913	1,142

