^{*} Sample size calculated using PROC POWER function in SAS with a two-sided likelihood ratio chi-square test, and the specified relative risk and prevalence in the unexposed (SAS EG V8.2, SAS Institute Inc., Cary, NC).

Table 2. Sample Size Required for 80% Power to Detect Relative Risks (As or More Extreme) for Infant Outcomes, with 1:2 Matching

Outcome	Prevalence of Outcome	RR	PAXLOVID- Exposed Livebirths Needed*	PAXLOVID- Exposed Pregnancies Needed**
MCM	3%	2	572	938
		2.5	294	482
Preterm birth	10%	2	153	251
		2.5	77	127
SGA	10%	2	153	251
		2.5	77	127

^{**} A divisor of 0.80, which is the proportion of ongoing pregnancies for which an outcome is eventually observed in DAPI, was used to calculate the number of exposed pregnancies needed.

Table 2. Sample Size Required for 80% Power to Detect Relative Risks (As or More Extreme) for Infant Outcomes, with 1:2 Matching

Outcome	Prevalence of	RR	PAXLOVID-	PAXLOVID-
	Outcome		Exposed	Exposed
			Livebirths	Pregnancies
			Needed*	Needed**

^{*} Sample size calculated using PROC POWER function in SAS with a two-sided likelihood ratio chi-square test and the specified relative risk and prevalence in the unexposed (SAS EG V8.2, SAS Institute Inc., Cary, NC).

Following initial accrual results from the first interim report, it was observed that fewer Cohort 2 pregnancies were accrued than PAXLOVID-exposed pregnancies, at a ratio of approximately 5:1, suggesting that matching of 2 comparators to each PAXLOVID pregnancy is unlikely to be feasible. Assuming a final ratio of 5 PAXLOVID-exposed pregnancies to each Cohort 2 pregnancy, a minimum sample size of 3,352 PAXLOVID-exposed pregnancies (and 670 Cohort 2 pregnancies) will be required to be accrued during the first trimester exposure window to detect a RR \geq 2.0 at 80% power for MCM. To detect a RR \geq 2.5, 1,664 PAXLOVID-exposed pregnancies (and 333 Cohort 2 pregnancies) will be required.

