Table 3 provides counts of total pregnancies, COVID-19 positive pregnancies, and pregnancies exposed to COVID-19 treatments within the ORD in 2020-2022. While 200,000 pregnancies are typically identified in any given calendar year within the ORD, this number has dropped slightly during the COVID-19 pandemic, as seen in Table 3 with roughly 180,000 pregnancies identified in 2020 and 2021. The counts include complete data through mid-2022; thus, some pregnancies in the latter half of 2022 may not be captured. Between 2020 and mid-2022, 35,303 of 460,062 pregnancies (7.7%) had a COVID-19 diagnosis code. Of the 35,303 COVID-19 positive pregnancies, 409 (1.2%) of pregnancies were exposed to bebtelovimab, while 382 (1.1%) were exposed to remdesivir. A total of 1,021 pregnancies were exposed to PAXLOVID, with roughly half of these also being diagnosed with COVID-19.

Annual interim reports will provide information on the uptake of PAXLOVID and the ability to reach adequate sample size for the study outcomes. If needed, a data partner may be added to increase statistical power (Section 9.4.4) to conduct the comparative analysis of MCM, per the secondary study objective. Even with multiple data partners, power may not be adequate for the assessment of stillbirth due to its rarity.

Table 3. Counts of Total and COVID-19 Positive Pregnancies in the Optum Research Database, 2020-2022

	2020	2021	2022	Total
			(partial) ^a	
All pregnancies	182,835	179,058	98,169	460,062

^{**} A divisor of 0.61, which is the proportion of ongoing pregnancies for which an outcome is eventually observed and the outcome is a livebirth in DAPI, was used to calculate the number of total exposed pregnancies needed.

^{***}Minimum sample size refers to the pregnancies with first trimester exposure

Table 3. Counts of Total and COVID-19 Positive Pregnancies in the Optum Research Database, 2020-2022

	2020	2021	2022	Total
			(partial) ^a	
Pregnancies with ≥1 PAXLOVID		295	726	1,021
dispensing				
Pregnancies with ≥1 COVID-19	10,337	19,581	5,385	35,303
diagnosis code				
Subset of pregnancies with ≥1		185	379	564
COVID-19 diagnosis code and ≥1				
PAXLOVID dispensing				
Subset of pregnancies with ≥1		184	225	409
COVID-19 diagnosis code and ≥1				
bebtelovimab administration				
Subset of pregnancies with ≥1	165	206	11	382
COVID-19 diagnosis code and ≥1				
remdesivir administration				

a Data for 2022 is approximately complete through June 2022.

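### Induced termination cannot have power similar to spontaneous abortion (SA) on the plan's own database divisors: 127 exposed pregnancies give about 56–59%, not 80%

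*Protocol*

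**What the plan says.** All of this is in the protocol; no SAP is at hand.

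- Section 9.5 lists approximate literature prevalences: "14% of pregnancies result in SA or miscarriage", "18% of pregnancies have historically been expected to end in induced termination" and "Under 1% of pregnancies result in stillbirth". It then says that the calculations use these prevalences.
- Table 1 has rows for SA (14%) and stillbirth (1%) only. For SA at RR 2 it gives 101 exposed pregnancies with an observed outcome, or 127 exposed pregnancies in all. The step from 101 to 127 is "A divisor of 0.80, which is the proportion of ongoing pregnancies for which an outcome is eventually observed in DAPI".
- Table 2 moves from livebirths to pregnancies with "A divisor of 0.61, which is the proportion of ongoing pregnancies for which an outcome is eventually observed and the outcome is a livebirth".
- For induced termination the only sizing statement is "Power for the analysis of induced termination will be similar to that for SA".
- Section 9.4.2 describes the database's yearly pregnancies as those "of which 80% (with observed outcomes) result in livebirths".
- Section 9.5 makes the RR 2 sample sizes the condition for running each comparative analysis. Table 4 lists induced termination as an outcome with its own prevalence ratio.

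**The concern.** The similarity statement looks safe beside a cited termination prevalence of 18%, which is higher than the 14% for SA. But 14%, 18% and 1% add up to 33% non-livebirths, while the two database divisors leave room for about 24% among the pregnancies whose outcome is seen, and Section 9.4.2 for 20%. The analysis can only count observed outcomes, so this room limits how common termination can be in the study data. If SA takes its 14%, termination must be well below 14%, and a comparison sized as for SA would be short of power. Termination has no threshold of its own in a section whose tables serve as entry conditions, so a reader would naturally carry the SA figure over to it.

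**Working it through.** **Inputs (Section 9.5 unless stated).** Two-sided alpha 0.05, power 0.80, RR 2, one exposed to two comparators, SA 14%, stillbirth 1% (Table 1), divisors 0.80 and 0.61, and an 80% livebirth share (Section 9.4.2). The test is a "two-sided likelihood ratio chi-square test, and the specified relative risk and prevalence in the unexposed".

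**Reproducing the plan's figure.** A likelihood-ratio chi-square calculation returns the printed 101 for SA exactly when the doubled prevalence is placed on the larger comparator arm, and 101/0.80 rounds up to 127. With the doubled prevalence on the exposed arm it returns 96. That is a separate matter. Below, results are given as a range or pair covering both placements, since the conclusion is the same under each.

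**Room for non-livebirths among observed outcomes.**
- Livebirth share from the divisors: 0.61/0.80 = 0.7625.
- Non-livebirths: 1 - 0.7625 = 23.75%.
- Less 1% stillbirth: 22.75% for SA and termination together.
- Less 14% SA: 8.75% for termination.
- On Section 9.4.2: 20% - 1% - 14% = 5% for termination.

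These are ceilings, because any further outcome category would reduce them. Stillbirth is described as under 1%. Setting it to zero raises the first ceiling only to 9.75%.

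**Power at 101 observed exposed pregnancies, and the number needed for 80%.**

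| Outcome prevalence in comparators | Power at 101 | Observed exposed needed | Exposed pregnancies needed (divided by 0.80) |
|---|---|---|---|
| 14% (SA) | 80–82% | 96–101 | 120–127 |
| 8.75% (termination, from divisors) | 56–59% | 167–178 | 209–223 |
| 5% (termination, from Section 9.4.2) | 34–36% | 310–332 | 388–415 |

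**Can another split rescue the statement?** At 101 observed, 80% power needs a prevalence of at least 13.4% with the doubled risk on the exposed arm, or 14.0% on the plan's calculation. For SA and termination both to reach this, plus 1% stillbirth, non-livebirths would have to be at least 2 × 13.4% + 1% = 27.7% (28.9% on the plan's calculation, from unrounded values), against 23.75% available. The most even split, 22.75%/2 = 11.4% each, gives 69–72% power for both. Scaling 14/18/1 down to 23.75% gives SA 10.1% (63–66% power) and termination 13.0% (76–78%). So at least one of the two outcomes falls short at 127 under every split.

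**The case against.** The strongest reply has four parts.

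1. *The tabulated inputs agree with one another.* SA 14% plus stillbirth 1% is 15%, which fits inside 23.75%. The conflict appears only when termination is added, and the 18% is described as historical, is approximate, and feeds no printed number. This stands, and it confines the point to the termination sentence.

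2. *If termination really is 18%, the statement errs on the safe side.* At 18%, only 87–92 exposed pregnancies are needed. This is correct, but 18% beside 14% SA cannot be the observed mix in a database that yields 0.80 and 0.61.

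3. *A reader might infer that the conflict also makes 938 too small for major congenital malformation,* by keeping 14/18/1 and replacing 0.61 with 0.80 × 0.67 = 0.536. The protocol does not support that step. It assumes that the 20% of pregnancies with no observed outcome have the same mix as the rest, which the protocol nowhere says; Section 9.7.4.3 treats differences between these groups as something still to be examined. With 67% livebirths overall, 61% observed livebirths leaves 6% unobserved livebirths and 14% unobserved non-livebirths, which together are exactly the 20% unobserved. So 0.61 and a 33% overall non-livebirth share can coexist. The observed share would still be 23.75%, so the termination point is unaffected.

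4. *The practical effect is small.* Table 3 already counts 1,021 PAXLOVID-exposed pregnancies by mid-2022, before eligibility criteria, well above 223 and also above 415. At 1:2 and 80% observed, that number would give over 99% power for RR 2 at either 8.75% or 5%. This largely stands for the full-pregnancy window against Cohort 3. Against Cohort 2, the roughly 5:1 accrual ratio that Section 9.5 reports is the tighter limit, and it is not examined here for termination. It is also an inference, not a stated rule, that termination opens on the SA figure.

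**Conclusion.** The similarity statement for induced termination is contradicted by the plan's own database figures. If SA is 14% and stillbirth 1%, termination among observed outcomes is at most about 8.75%, or 5% by Section 9.4.2. Power at 127 exposed pregnancies is then about 56–59% (34–36%), and 209–223 (388–415) are needed. This rests on RR 2, 1:2 allocation, the plan's test, and 0.61/0.80 being the livebirth share of observed outcomes as the footnotes define it.

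It would go too far to say that either the SA figure of 127 or the malformation figure of 938 must be wrong. Both are consistent with the inputs used to derive them, and this argument does not show either to be in error.

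Severity is minor: one secondary outcome carries an unsupported power statement, and accrual makes it unlikely that the full-pregnancy comparison with Cohort 3 is affected.

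**What to change.** In Section 9.5:

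- Add an induced-termination row to Table 1, at the prevalence observed in the database among pregnancies with an outcome, so that its entry condition is explicit. If SA is 14% and the divisors hold, expect a minimum no lower than about 209–223 exposed pregnancies.
- Delete the sentence that equates its power with that for SA, or replace it with the calculated figure.
- Say that the 18% is a historical national figure that is not used for sizing, or drop it.
- Reconcile the 76% livebirth share implied by 0.61/0.80 with the 80% in Section 9.4.2, which would imply a divisor of 0.80 × 0.80 = 0.64. If the 80% there is really the share with an observed outcome, reword that sentence.

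The SA and malformation rows need no change on this account. The cost is one recalculation from outcome counts that the data holder should already have, and a short text edit. No additional data are needed. The restated termination minimum will probably be higher than 127.

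### The Section 9.5 sample sizes match only a calculation with the two groups transposed, and the infant targets omit 85% linkage, so the Cohort 2 MCM target of 3,352/670 has about 74% power (67% after linkage), not 80%

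*Protocol*

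**What the plan says.** Protocol Section 9.5 fixes alpha 0.05, power 0.8, a 1:2 ratio of exposed to comparator, and reference prevalences of 14% (SA), 1% (stillbirth), 10% (preterm birth, SGA) and 3% for MCM: "3% of live born infants have a major birth defect in the US each year". The table footnotes give the method: "Sample size calculated using PROC POWER function in SAS with a two-sided likelihood ratio chi-square test", with "the specified relative risk and prevalence in the unexposed". On this basis the text states: "A minimum of 938 PAXLOVID-exposed pregnancies during the first trimester are required for the primary outcome of MCM".

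After the first interim report showed about five PAXLOVID pregnancies per Cohort 2 pregnancy, "suggesting that matching of 2 comparators to each PAXLOVID pregnancy is unlikely to be feasible", the section adds a 5:1 calculation for MCM. At a relative risk of 2.0, "a minimum sample size of 3,352 PAXLOVID-exposed pregnancies (and 670 Cohort 2 pregnancies) will be required"; at 2.5 the figures are 1,664 and 333.

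Livebirths are converted to pregnancies in Table 2 with this factor: "A divisor of 0.61, which is the proportion of ongoing pregnancies for which an outcome is eventually observed and the outcome is a livebirth". Section 9.4.2 says of livebirths: "85% of which can be linked to an infant within the database". Section 9.7.2.2 and Table 4 make linked livebirths the denominator for every infant outcome.

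**The concern.** Two separate faults affect the same numbers.

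- **Orientation.** The footnotes place the reference prevalence in the unexposed. The stated counts behave as if it had been placed in the exposed. With unequal groups this matters, and the direction depends on which group is larger: mildly conservative at 1:2, anti-conservative at 5:1.
- **Linkage.** The pregnancy targets for infant outcomes allow for unobserved outcomes and non-livebirths, but not for the 15% of livebirths that cannot be linked and so never enter the analysis.

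Section 9.5 makes reaching the target for a relative risk of 2.0 the condition for each comparative analysis. Sections 9.4.4, 9.5 and 9.7.1 use accrual against need, reviewed after the third interim report, to decide on a data partner and on lengthening or shortening accrual. A target that is too low could let the MCM comparison proceed, or accrual stop, with power well under the stated 80%. In a safety study that raises the chance of a falsely reassuring null result.

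**Working it through.** **Formula.** For the likelihood-ratio chi-square test with group shares w₁, w₂, risks p₁, p₂ and pooled risk p̄ = w₁p₁ + w₂p₂, the noncentrality is N·d, where

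d = 2·Σ wᵢ [pᵢ ln(pᵢ/p̄) + (1 − pᵢ) ln((1 − pᵢ)/(1 − p̄))].

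With 1 degree of freedom, two-sided alpha 0.05 and 80% power, N·d must equal 7.849.

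**Tables 1 and 2, smaller group at 1:2 (before the divisors).** *As described* means exposed is the smaller group and carries the raised risk. *Transposed* means the smaller group carries the reference risk.

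| Outcome, RR | Stated | As described | Transposed |
|---|---|---|---|
| SA, 2.0 | 101 | 95.3 | 100.8 |
| SA, 2.5 | 50 | 46.4 | 49.7 |
| Stillbirth, 2.0 | 1,769 | 1,642.4 | 1,769.0 |
| Stillbirth, 2.5 | 913 | 828.4 | 912.2 |
| MCM, 2.0 | 572 | 531.7 | 571.4 |
| MCM, 2.5 | 294 | 267.1 | 293.1 |
| Preterm/SGA, 2.0 | 153 | 142.9 | 152.1 |
| Preterm/SGA, 2.5 | 77 | 70.6 | 76.3 |

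Rounded up, the transposed column gives all eight stated figures; the column as described gives none.

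**5:1, MCM, RR 2.0: the plan's figure first.** Put the 3% risk on the group of five and 6% on the group of one: p̄ = 0.035, d = 0.003203, N = 2,450.6. Rounded up to a multiple of six, N = 2,454 = 2,045 + 409. Then 2,045/0.61 = 3,352 and 409/0.61 = 670, as printed. At RR 2.5 the same route gives 1,218 = 1,015 + 203, hence 1,664 and 333, as printed.

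**5:1 as described.** PAXLOVID is the group of five at 6%, Cohort 2 the group of one at 3%: p̄ = 0.055, d = 0.002771, N = 2,832.4, rounded up to 2,838 = 2,365 + 473. At RR 2.5: N = 1,464.6, rounded up to 1,470 = 1,225 + 245.

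| RR | Stated pregnancies | Correct, ÷ 0.61 | With linkage, ÷ 0.5185 |
|---|---|---|---|
| 2.0 | 3,352 / 670 | 3,878 / 776 | 4,562 / 913 |
| 2.5 | 1,664 / 333 | 2,009 / 402 | 2,363 / 473 |

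Here 0.5185 = 0.61 × 0.85. At RR 2.0 the stated target is low by (3,878 − 3,352)/3,878 = 14% from orientation alone, and by (4,562 − 3,352)/4,562 = 27% with linkage.

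**Power of the stated 5:1 targets, correctly oriented (likelihood-ratio approximation).**

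- 3,352/670, RR 2.0: 74% after 0.61; 67% after 0.5185.
- 1,664/333, RR 2.5: 72% and 65%.

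The Pearson approximation at 3,352/670 gives 72% and 64%. Exact enumeration at 2,045/409 livebirths gives 77% for the likelihood-ratio test and 73% for Pearson; after linkage, 70% and 65%.

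**1:2 infant outcomes, correctly oriented and linked.** MCM: 532/0.5185 = 1,027 (stated 938); at RR 2.5, 268/0.5185 = 517 (stated 482). Preterm/SGA: 143/0.5185 = 276 (stated 251); at RR 2.5, 71/0.5185 = 137 (stated 127). The 572 MCM livebirths behind 938 have 83% power; 85% of them have 76%.

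**Table 1, where linkage does not apply.** SA: 96/0.80 = 120 (stated 127) and 47/0.80 = 59 (stated 63). Stillbirth: 1,643/0.80 = 2,054 (stated 2,212) and 829/0.80 = 1,037 (stated 1,142).

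**The case against.** - **The cause is inferred.** No program code is shown. This stands as a caveat, but ten matches out of ten leave little doubt, and the conclusion does not need the cause: the printed figures do not follow from the printed inputs.
- **The swap is conservative in Tables 1 and 2.** True. Only the 5:1 pairs are too low because of it; the shortfall at 938 comes from linkage alone.
- **The loss depends on how power is computed.** True. For orientation alone, power at 3,352/670 runs from 72% (Pearson approximation) to 77% (exact, likelihood-ratio). Every version is under 80%.
- **Linkage is disclosed.** The divisor is openly defined, and Section 9.5 ends with a note that incomplete linkage could change the final size. The note changes no target, although the 85% was at hand and the tables already apply a loss factor.
- **The gate cites Tables 1 and 2, comparison is a secondary objective, and other checks exist.** Interim reports 2-4 give effective sample sizes under the weights, and power is reassessed after the third. These soften the consequence. Still, the 5:1 paragraph presents its counts as a required minimum, and that review would measure accrual against them.
- **Weighting retains all pregnancies, so 1:2 is conservative.** This does not help at 5:1, where all accrued pregnancies are already counted.

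**Conclusion.** The concern holds. The Section 9.5 counts contradict their own footnotes, and the infant targets use a denominator different from the planned analysis. For the Cohort 2 comparison on MCM, 3,352/670 gives about 74% power before linkage and 67% after it; the requirement for 80% is 3,878/776 and 4,562/913 respectively. The 938 target gives about 76% once linkage is counted. The Table 1 targets are somewhat too high, by 6% to 10%.

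This rests on the protocol's own test, 3% reference prevalence, 5:1 ratio, divisor 0.61 and 85% linkage, with linkage taken as equal in both cohorts. Losses from weighting and from incomplete record retrieval are not included. Pregnancy counts are rounded up; rounding to the nearest integer gives 3,877/775 and changes nothing of substance.

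**What to change.** Re-run the calculation with the comparator as the reference group: reference-to-exposed weights of 2:1 for Tables 1 and 2, and 1:5 for the Cohort 2 case. For infant outcomes, divide by 0.61 × 0.85 = 0.5185 and define that factor in the Table 2 footnote. Then restate Tables 1 and 2, the abstract and the 5:1 paragraph:

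- Cohort 2, MCM: 4,562/913 at RR 2.0 and 2,363/473 at RR 2.5 (before linkage, 3,878/776 and 2,009/402).
- 1:2, MCM: 1,027 and 517. Preterm birth and SGA: 276 and 137.
- SA: 120 and 59. Stillbirth: 2,054 and 1,037.

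Use one rounding rule throughout; the tables round up, while the 5:1 pregnancy counts were rounded to the nearest integer.

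The cost is one re-run and protocol wording. The correction does not itself change accrual, but the higher MCM targets bear on the data-partner and accrual decisions, so it should be in place before the review after the third interim report, planned for March 2026.
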